Confirmatory Study: Assessing the Efficacy and Safety of the AcusMu Microneedle Patch in Treating Periorbital Wrinkles

NCT06158867

Date: 1st August, 2024

Study Protocol

1. Objective

We have developed a microneedle patch infused with Argireline, with the aim of providing a user-friendly, effective, and safe at-home treatment for under-eye wrinkles. Despite the potential benefits, the efficacy and safety of this novel patch have not yet been investigated in patients with mild to moderate under-eye wrinkles. Therefore, we conducted a split-face, double-blind, randomized, placebo-controlled clinical trial to evaluate the effectiveness and safety of this product in improving under-eye wrinkles.

2. Design

This trial was designed as a prospective, randomized, controlled, double-blinded, single-center study. A split-face design was employed to compare the effects of microneedle patches with and without anti-wrinkle ingredients on patients with under-eye wrinkles. Subjects applied the test products daily, using either product A (microneedle patches containing active anti-wrinkle ingredients) or product B (placebo patches), to the under-eye area. The patches were pressed onto the skin with fingers 5-10 times and left in place for 8 hours before removal. The treatment was continued for 14 days.

Subjects visited the clinic at four time points: baseline (week 0), week 1, week 2, and week 4 (± 2 days). During each visit, two independent and blinded dermatologists evaluated the under-eye wrinkles using photographs based on the wrinkle grading scale, calculating the wrinkle improvement index. These evaluations were complemented by the subjects' self-assessment questionnaires to understand the efficacy of the microneedle patches with anti-wrinkle ingredients compared to the placebo patches over two weeks (assessments at weeks 0, 1, 2, and 4). Throughout the study period, subjects were advised to continue using their usual cosmetics and avoid changing any products. Any discomfort or adverse events experienced by the subjects were reported during the study.

3. Methods

3.1 Subjects

This prospective study was approved by the Institutional Review Board (IRB) of Taipei Medical University (TMU-JIRB No. N202308044). Informed consent was voluntarily and appropriately obtained from all subjects. The inclusion criteria for subjects were individuals aged between 18 and 99 years with clinician-assessed under-eye wrinkles of grade 2 or higher (mild or above). Exclusion criteria included subjects with open or infected wounds on the test skin area, participation in other studies that might interfere with this trial, pregnancy or breastfeeding, plans to become pregnant during the trial period, and major illnesses such as cancer, liver disease, diabetes, kidney disease, or cardiovascular disease. Subjects who had undergone other treatments for periorbital fine lines (e.g., laser, radiofrequency) within the past six months or who were concurrently undergoing such treatments were also excluded.

3.2 Microneedle patch

The microneedle (MN) patch applied to the under-eye area consisted of an adhesive hydrocolloid pad and

needles with a length of 300 μm . The experimental group's patches contained microneedles infused with Argireline at concentrations of 45 $\mu\text{g/g}$ (high concentration) and 15 $\mu\text{g/g}$ (low concentration). The control group's microneedles did not contain any active ingredients.

3.3 Grading of under-eye wrinkles

To evaluate under-eye wrinkles, a modified photonumeric grading scale developed by Jang et al. was utilized.¹⁹ This scale, based on the number of fine, moderate, and deep wrinkles, ranges from 0 to 4 (0: no wrinkles, 4: numerous distinct fine and moderate wrinkles with numerous deep wrinkles). The grading details are as follows: **Grades 0 (GR 0)**: no wrinkles; **Grade 1 (GR 1)**: a few distinct fine wrinkles; **Grade 1.5 (GR 1.5)**: a few distinct fine wrinkles with one or two moderate wrinkles; **Grade 2 (GR 2)**: numerous distinct fine wrinkles with a deep wrinkle confined to the medial side; **Grade 2.5 (GR 2.5)**: numerous distinct fine wrinkles with a few moderate wrinkles; **Grade 3 (GR 3)**: numerous distinct fine wrinkles with a deep wrinkle on both medial and lateral sides and/or indistinct under-eye bags; **Grade 3.5 (GR 3.5)**: numerous distinct fine wrinkles with three or four deep wrinkles and/or distinct under-eye bags; **Grades 4 (GR 4)**: numerous distinct fine, moderate, and deep wrinkles.

3.4 Subject Self-Assessment Questionnaire

Subjects self-assessed the improvement of under-eye wrinkles using a Visual Analogue Scale (VAS) at four different time points: week 0 (baseline), week 1, week 2, and week 4. This subjective evaluation aimed to reflect the treatment's efficacy based on the severity of wrinkles. The VAS scores ranged from 0 to 10, with 0 representing smooth, wrinkle-free skin and 10 indicating severe wrinkles. The questionnaire included a series of icons (Figure S1) depicting "very satisfied," "satisfied," "neutral," "dissatisfied," and "very dissatisfied" from left to right. Subjects were asked to answer the question, "Over the past week, how would you rate the severity of your under-eye wrinkles?" and to record separate scores for the left and right sides.

Statistical Analysis Plan

All statistical tests were conducted using R (version 4.3.3) with one-tailed Wilcoxon signed rank tests at a significance level of 0.05. Confidence intervals were calculated at a 95% confidence level, focusing on the intent-to-treat population. Longitudinal comparisons of microneedle patches and placebo patches were made at baseline, 7, 14, and 28 (± 2 days) days. Wilcoxon rank sum tests compared different concentrations of active ingredients. Changes during the trial were estimated using Generalized Estimating Equations (GEE). Results were visualized with bar plots using the R-packages ggpunr (version 0.6.0) and tidyverse (version 2.0.0), with standard errors presented as error bars.

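### The self-assessment asks for wrinkle severity but shows satisfaction icons and is described as improvement, so a change in the VAS may not be a pure change in severity

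*Combined protocol and SAP*

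**What the plan says.** Section 3.4 (Subject Self-Assessment Questionnaire) describes one instrument, completed at weeks 0, 1, 2 and 4, in three different terms.

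- **Severity.** The question is "Over the past week, how would you rate the severity of your under-eye wrinkles". The anchors agree with it: "The VAS scores ranged from 0 to 10, with 0 representing smooth, wrinkle-free skin and 10 indicating severe wrinkles". So does the stated aim: "This subjective evaluation aimed to reflect the treatment's efficacy based on the severity of wrinkles".
- **Satisfaction.** "The questionnaire included a series of icons (Figure S1") is how the icons are introduced, "depicting 'very satisfied,' 'satisfied,' 'neutral,' 'dissatisfied,' and 'very dissatisfied' from left to right".
- **Improvement.** The opening sentence reads "Subjects self-assessed the improvement of under-eye wrinkles using a Visual Analogue Scale (VAS) at four different time points".

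Subjects score the left and right sides separately. The Statistical Analysis Plan uses one-tailed Wilcoxon signed rank tests at 0.05 and estimates changes during the trial by GEE. It does not name the outcomes to which each method applies. I take the VAS to be among them. Section 2 (Design) describes the questionnaires as complementing photographic grading by two independent blinded dermatologists.

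**The concern.** Severity, satisfaction and improvement are different quantities. A subject with marked wrinkles may be content, and one with few may not be. Improvement needs an earlier state to compare with, so it cannot be rated at week 0, yet the VAS is scored then.

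The meaning of satisfaction may also move during the trial. At week 0 no patch has been used, so it can only concern appearance. At weeks 1, 2 and 4 it may also concern the product. If some subjects answer the icons instead of the question, a change from baseline compares two different things.

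At stake is the interpretation of the only subject-reported efficacy measure that the plan describes, for a product meant for use at home.

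**Working it through.** The documents give no sample size, power, effect size or SD for the VAS, so there is no planned figure to reproduce. The check has three parts.

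**1. The text side by side (Section 3.4).**

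| Element | Quantity |
|---|---|
| Question | severity |
| Anchors at 0 and 10 | severity |
| Stated aim | efficacy judged by severity |
| Icons | satisfaction |
| Opening description | improvement |

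Only one question is described. The icons either belong to it or to an item that the protocol does not mention. In both cases the text needs correcting.

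**2. What a satisfaction component would do.** Write score = (1 − w) × severity + w × satisfaction + noise, where w is the weight given to satisfaction.

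*Within-side change* = (1 − w) × (change in severity) + w × (change in satisfaction). With w = 0.25, no change in severity and satisfaction shifting by 1 point, the VAS moves by 0.75 × 0 + 0.25 × 1 = 0.25 points. Nothing removes this from a within-side trend.

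*Active-minus-placebo difference.* Satisfaction common to both sides cancels. The severity difference is multiplied by a = (1 − w) + w × rho, where rho is the side difference in satisfaction relative to that in severity. For power, I use Φ(a·d/√(a² + t²) × √(3n/π) − 1.645). The assumed values, none from the documents, are n = 30, d = 0.5 SD of the severity difference, and noise SD t = 0.5.

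| rho | w | a | Power |
|---|---|---|---|
| any | 0 | 1 | 77.3% |
| 0 | 0.25 | 0.75 | 72.0% |
| 0 | 0.5 | 0.50 | 59.8% |
| 1 | 0.25 or 0.5 | 1.00 | 77.3% |
| 1.5 | 0.25 | 1.125 | 78.8% |
| 1.5 | 0.5 | 1.25 | 80.0% |

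With t = 0, power is 84.9% in every row, because rescaling the differences does not alter a rank test. The side difference can shrink, stay the same or grow, depending on rho, w and t. The documents fix none of them.

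**3. Subjects who score both sides equally.** Suppose a share q does so. Their differences are zero, and the standard signed rank test drops zeros. The informative sample is n(1 − q), so the same power needs about 1/(1 − q) times as many subjects:

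- q = 0.2: 1/0.8 = 1.25
- q = 0.4: 1/0.6 = 1.67

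A simulation with assumed normal differences, n = 30 and d = 0.5 agrees. Power is about 83% without ties, and about 75% and 63% at q = 0.2 and 0.4. Raising n to 38 (30 × 1.25 = 37.5) and 50 (30/0.6) restores it.

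**The case against.** The case for leaving the plan alone has weight. The question, both anchors and the stated aim all concern severity. The icons run in the same direction as the scale if 0 is on the left. Subjects score each side separately, which works against a single whole-face answer. A drift in satisfaction common to both sides cancels in the treatment contrast, and two blinded graders working from photographs are untouched by the form. All of this limits the importance of the point. It does not explain the satisfaction labels or the word improvement, and cancellation does not help a within-side change.

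Three stronger readings are tempting, and the documents support none of them.

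- *A reader might infer that the icons are printed on the 0-10 line.* The text says only that the questionnaire included them. Figure S1, which would show the layout, is not reproduced in the text available here, and its absence is not a fault of the plan. That the score does mix severity with satisfaction is therefore a risk, not a documented fact.
- *A reader might infer that the side difference is diluted.* This needs satisfaction to be less side-specific than severity. Nothing in the documents says so.
- *A reader might infer a sample-size penalty of 1/(1 − q)², that is 1/0.64 = 1.56 to 1/0.36 = 2.78 for q of 20% to 40%.* That formula shrinks the mean difference but holds the SD fixed. Equal side scores are exact zeros, which the test drops, so 1/(1 − q) applies, and q itself is assumed.

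**Conclusion.** The mismatch holds: the response icons and the description of the outcome do not match the question and its anchors, and no separate satisfaction item is described. The consequence is one of interpretation. A change in VAS, especially a within-side change over time from the GEE, may partly reflect satisfaction.

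No size or direction can be given for an effect on the active-minus-placebo difference, and no loss of power or need for more subjects should be claimed. The ratio of 1.25 to 1.67 only shows what would follow from an assumed 20% to 40% of subjects scoring both sides alike, under a signed rank test that discards zeros. The conclusion on interpretation does not depend on those assumptions. The point is modest because the blinded photographic grading is unaffected, but it is worth acting on because the remedy is nearly free.

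**What to change.** - Replace the satisfaction icons with severity labels running from smooth to severe, or remove them from the severity item. Keep the question.
- If satisfaction is wanted, ask it as a separate item for each side, at post-baseline visits only.
- In Section 3.4 and the Statistical Analysis Plan, define and analyse the VAS as self-rated severity and its change, and drop the word improvement. State what role, if any, the icons have in scoring.
- The protocol is written in the past tense. If data were already collected with the icons, disclose the icon labels and report the VAS as supportive to the blinded photographic grading.

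The cost is a small change to the form and wording or, for data already collected, a change to reporting only. It needs no additional subjects or new analysis method.

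### A trial titled confirmatory tests active against placebo at three visits at one-tailed 0.05, with no primary endpoint, primary visit, testing order or multiplicity rule

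*Combined protocol and SAP*

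**What the plan says.** The title reads "Confirmatory Study: Assessing the Efficacy and Safety of the AcusMu Microneedle Patch". Section 1 (Objective) says that "the efficacy and safety of this novel patch have not yet been investigated in patients with mild to moderate under-eye wrinkles".

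Section 2 (Design) describes daily patch use and states: "The treatment was continued for 14 days". At each visit, "two independent and blinded dermatologists evaluated the under-eye wrinkles using photographs based on the wrinkle grading scale, calculating the wrinkle improvement index". Self-assessment is introduced with "These evaluations were complemented by the" subjects' questionnaires, and the purpose is given as learning the "efficacy of the microneedle patches with anti-wrinkle ingredients compared to the placebo patches over two weeks (assessments at weeks 0, 1, 2, and 4"). Section 3.4 collects a 0-10 VAS for each side at the same visits. Section 3.2 says the experimental "patches contained microneedles infused with Argireline at concentrations of" 45 and 15 µg/g.

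The Statistical Analysis Plan is one paragraph. It sets one-tailed signed rank tests at 0.05 and states: "Longitudinal comparisons of microneedle patches and placebo patches were made at baseline, 7, 14, and 28 (± 2 days) days". It adds rank sum tests between concentrations and a GEE to estimate change over time. Nothing in it says which measure, visit or analysis decides efficacy.

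**The concern.** A level of 0.05 describes one test. It describes the efficacy claim only if the plan says which test, or which combination of tests, makes the claim. Here there are at least three candidates (one measure at days 7, 14 and 28). There are six if the VAS is tested alongside the grade, which the SAP neither says nor excludes.

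Other choices are open too:
- whether the endpoint is the raw grade, its change from baseline or the improvement index;
- how the two dermatologists' grades are combined;
- whether the two concentrations are pooled against placebo;
- whether the GEE or the visit-by-visit tests decide.

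With no success rule, each of these can be settled after the results are known. A trial presented as confirmatory should rule that out.

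**Working it through.** **Inputs from the documents.** Level 0.05, one-tailed, per test. Post-baseline comparison days: 7, 14 and 28. The baseline comparison is not an efficacy test and is left out. Measures collected: dermatologist grade and VAS.

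**Assumptions.** All nulls are true, any single significant result counts as efficacy, and concentrations are pooled. Correlation of the test statistics between visits r = 0.5-0.9, and between measures o = 0-0.9. The documents give neither the correlations nor a sample size.

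**1. The plan's own figure.** One test: 1 − 0.95 = 0.05. The stated level is exact for one test.

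**2. Independent tests.** Three tests: 1 − 0.95³ = 0.143. Six tests: 1 − 0.95⁶ = 0.265.

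**3. Correlated tests.** Error = 1 − P(all Z ≤ 1.645), with Z multivariate normal. The correlation is r between visits, o between measures, and the product r × o across both.

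| Tests | r | o | Any-hit error |
|---|---|---|---|
| 3 | 0.5 | – | 11.8% |
| 3 | 0.7 | – | 10.3% |
| 3 | 0.9 | – | 8.0% |
| 6 | 0.5 | 0 | 22.3% |
| 6 | 0.5 | 0.5 | 19.9% |
| 6 | 0.9 | 0.5 | 13.6% |
| 6 | 0.9 | 0.9 | 10.6% |

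As multiples of 5%, this is 1.6 to 2.4 for three tests and 2.1 to 4.5 for six. A correlation that decays with the gap between visits (AR(1), 0.5-0.9) gives 12.3% to 8.3% for three tests.

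**4. Discrete scores.** Signed rank tests were simulated on rounded scores with assumed SDs and step sizes (20,000 trials per scenario; (r, o) = (0.5, 0) and (0.9, 0.8)).
- n = 20 and 40: three tests 7.1-12.1%, six tests 12.4-22.7%.
- n = 10, lighter ties: three tests 7.6-10.4%, six tests 11.5-19.6%.
- n = 10, heavy ties: each test's own size falls to 1.8-2.9%, three tests give 4.0-7.3%, six tests 7.8-12.0%.

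**5. Naming a visit is not enough.** Suppose day-14 grade is named but raw value or change from baseline can still be chosen. With baseline correlated r with day 14, the two statistics correlate (1 − r)/√(2(1 − r)) = √((1 − r)/2). This is 0.50 at r = 0.5 and 0.22 at r = 0.9. The chance that at least one is significant is then 8.8% and 9.4%, not 5.0%.

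**6. The remedies.** One fully defined primary test gives 5.0%. For Holm over six change-from-baseline tests the first step is 0.05/6 = 0.0083. Change scores correlate 0.5 between visits at any r, because (1 − r)/(2(1 − r)) = 0.5. The familywise error is then 4.4% at o = 0 and 3.2% at o = 0.9. If raw or change can still be chosen, it is 5.2-8.1%.

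Power at that step for a test with 80% power at one-sided 0.05: 1 − Φ(2.394 − (1.645 + 0.842)) = 0.537. For 90%: 1 − Φ(2.394 − (1.645 + 1.282)) = 0.703.

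**The case against.** The strongest reply is that the documents never say one significant visit would establish efficacy. What they prove is an unspecified success rule, not a doubled error rate. That is fair as far as it goes: the omission is certain, and the percentages are conditional on the decision rule, the correlations and the sample size. But nothing in the plan excludes the any-hit reading, and that absence is the defect. The wording about complementing the grading and about two weeks leans towards dermatologist grade at day 14. It does not designate either, and weeks 0, 1, 2 and 4 are listed in the same sentence.

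Ties are a real limit. Section 3.3 defines eight grade levels, mostly in half-grade steps, and with 10 subjects and heavy ties the three-test error may be no more than 5%. With no stated sample size the plan cannot rely on that.

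Nor are six tests a ceiling. If each concentration were tested separately in independent subjects (an assumption), one measure would give 1 − (1 − 0.0795)² = 15% to 1 − (1 − 0.1184)² = 22%. Two measures would give 1 − (1 − 0.1061)² = 20% to 1 − (1 − 0.2228)² = 40%.

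The confirmatory label appears only in the title, and the Objective reads more like a first efficacy study. Dropping the label and reporting estimates with intervals would remove that tension, but would also give up the claim of efficacy at the 5% level.

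Finally, averaging graders, subtracting baseline and pooling concentrations are proposals, and the first two treat the ordinal grade as interval. Another single definition would serve, provided it is fixed without sight of the results.

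**Conclusion.** The concern holds and must be fixed. The missing primary endpoint, visit, order and success rule is a matter of text and is not in doubt. Its size depends on the assumptions above. Under the any-hit rule, error is about 8-12% for one measure at three visits (14.3% if independent) and about 11-22% for grade and VAS together (26.5% if independent). The direction is robust for continuous data, because the error exceeds 5% unless the tests are perfectly correlated. The exception found is a very small sample with heavy ties. Tests of the improvement index and concentration-specific tests are not counted in these ranges.

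**What to change.** First state in the SAP whether unblinded results have been seen. The text is in the past tense and does not settle this.

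**(a) If not seen.** Name one primary test: the within-subject active-minus-placebo difference in change from baseline in dermatologist grade at day 14, using the mean of the two graders, concentrations pooled, at the stated level. Day 14 is proposed because treatment ends then and Section 2 frames efficacy over two weeks; the documents do not themselves rank week 4 lower. Then test in fixed order, stopping at the first non-significant result: day-28 grade, day-14 VAS, day-28 VAS, all as change from baseline, active minus placebo, pooled. Report day 7, the improvement index and the comparison between concentrations as estimates with intervals.

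**(b) If seen.** Do not name a primary now. Apply Holm across six tests (grade and VAS at days 7, 14 and 28, with the same definitions). Label the index and concentration comparisons exploratory. State that an adjustment chosen after seeing results limits the error but does not fully restore 5% control.

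In both cases, state that the GEE is supportive estimation and that the baseline comparison is descriptive.

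**Cost.** SAP wording only, no new data. Isolated significant results outside the tested family no longer support an efficacy claim. Under (a) the primary test keeps the full 0.05. Under (b), at Holm's strictest step, 80% power becomes about 54% and 90% becomes about 70%.

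### No reading of the SAP gives a baseline-adjusted active-versus-placebo comparison, so stable left-right asymmetry may be left in the side difference as avoidable noise

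*Combined protocol and SAP*

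**What the plan says.** The trial is split-face, with an active patch on one side and placebo on the other. Section 2 (Design) sets the visits: "Subjects visited the clinic at four time points: baseline (week 0), week 1, week 2, and week 4". At each visit two blinded dermatologists grade the wrinkles from photographs, "calculating the wrinkle improvement index"; no formula is given and the SAP does not mention the index. In section 3.4 subjects rate severity on a 0-10 VAS at the same four times and are asked "to record separate scores for the left and right sides".

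The SAP is one paragraph. On this point it says:

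- The tests are "one-tailed Wilcoxon signed rank tests at a significance level of 0.05".
- For active against placebo it states: "Longitudinal comparisons of microneedle patches and placebo patches were made at baseline". The three follow-up visits are then listed in the same sentence, so baseline stands as one comparison visit among four.
- For high against low strength it states: "Wilcoxon rank sum tests compared different concentrations of active ingredients". No outcome variable is attached to this test.
- The only reference to change is this: "Changes during the trial were estimated using Generalized Estimating Equations (GEE").

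It does not say whether the tests use visit scores, changes from baseline or the index. It names no baseline covariate. For the GEE it gives no outcome, model terms, contrast or working correlation.

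**The concern.** In a split-face trial the inference rests on the active-minus-placebo difference within each subject. Pairing removes overall severity but not a subject's stable left-right asymmetry. Section 3.1 requires grade 2 or higher and states no symmetry requirement, so asymmetry can be present at entry.

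A change from baseline is zero at baseline by definition. Listing baseline as a comparison visit therefore suggests raw visit scores, though this is an inference. If raw scores are tested, all the asymmetry stays in the difference.

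If the index, or a GEE with baseline as one of the visits, amounts to a difference in change, asymmetry is removed but baseline measurement error is added. That loses power when baseline and follow-up side differences are weakly correlated.

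The input to the rank-sum test between concentrations is not stated either. If it is the raw active-side score, it also carries the whole between-subject spread in severity.

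**Working it through.** **Inputs.** From the SAP: one-sided alpha 0.05 and signed-rank tests. From section 3.3: grade steps 0, 1, 1.5 and so on to 4. The documents give no sample size, SD, effect size or correlation, so there is no planned figure to reproduce, and every other input below is assumed.

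**Variance of the side difference.** Let D0 and D1 be the active-minus-placebo differences at baseline and follow-up, with equal variance and correlation r. Relative to raw D1 (variance 1):

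- difference in change, D1 − D0: 2(1 − r)
- D1 adjusted for D0: 1 − r²

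Since 2(1 − r) − (1 − r²) = (1 − r)², adjustment is never worse than change in large samples. Change beats raw only when r > 0.5.

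Subjects needed for 80% power, with an assumed effect of 0.5 SD of the raw difference, are ((1.645 + 0.842)/0.5)² = 24.7 times the relative variance, rounded up:

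| r | Variance: change | Variance: adjusted | n: raw | n: change | n: adjusted |
|---|---|---|---|---|---|
| 0.3 | 1.40 | 0.91 | 25 | 35 | 23 |
| 0.5 | 1.00 | 0.75 | 25 | 25 | 19 |
| 0.7 | 0.60 | 0.51 | 25 | 15 | 13 |

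**Simulation on the trial's grade steps.** 4,000 runs per setting, n = 30, effect 0.2 grade, between-subject SD 0.5. Side SD / visit-error SD, from the top row down: 0.35/0.15, 0.35/0.25, 0.25/0.25, 0.15/0.25, 0/0.25. The r shown is that after rounding to grades. In the last column each side's own baseline score is the covariate, with independence working correlation.

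| r | Power %: raw / change / adjusted | SE: raw / change / adjusted | SE: own-side baseline |
|---|---|---|---|
| 0.73 | 58 / 82 / 85 | 0.104 / 0.075 / 0.072 | 0.072 |
| 0.58 | 50 / 58 / 65 | 0.116 / 0.104 / 0.095 | 0.097 |
| 0.42 | 62 / 57 / 68 | 0.098 / 0.104 / 0.090 | 0.095 |
| 0.21 | 76 / 58 / 76 | 0.083 / 0.105 / 0.082 | 0.094 |
| 0 | 83 / 59 / 82 | 0.074 / 0.104 / 0.076 | 0.092 |

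With no effect, the raw test rejected in 4.6-4.9% of runs and the adjusted analysis in 4.8-4.9%. The matter is precision, not bias.

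The last column shows that the form of adjustment matters. Own-side baseline alone is less precise than raw scores at r of 0.21 or below, because its slope mixes between-subject and within-subject information (pooled slope 0.76 against a within-subject slope of 0.22 at r = 0.21). Entering the two parts as separate terms gave the same SE as the difference-on-difference regression in every setting.

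**Chance imbalance.** Only r times a baseline imbalance carries over to follow-up. With a side-difference SD of 0.5 grade and n = 30, a one-SE imbalance is 0.5/√30 = 0.09 grade. It carries 0.027, 0.046 or 0.064 grade at r = 0.3, 0.5 or 0.7, which is 14, 23 or 32% of a 0.2-grade effect.

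**Concentrations.** With 15 per group, a 0.3-grade difference and r of about 0.2 to 0.7, power was 30-36% for a rank-sum test on raw active-side scores and 45-64% for the adjusted side difference. A rank-sum test on active-side change gave 60-82%, but it has no placebo control and the simulation has no subject-level drift between visits.

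**The case against.** - **The raw-score reading is not proven.** Baseline could be listed as the reference for within-patch tests of each later visit, and the index or the GEE may use baseline. This stands, so the loss from asymmetry is conditional. But none of these readings yields a baseline-adjusted contrast between sides.
- **The largest gain may not apply.** The 27 points at r = 0.73 come from the most favourable of five settings and are measured against raw scores. If the real analysis is a difference in change, the gain there is 3 points, and 7 to 11 points at r = 0.58 and 0.42. With small asymmetry (side SD and error SD both 0.15), raw power was 91% and adjusted 93%. This stands too.
- **The simulation uses one rater.** The trial has two, and how they are combined is not stated. Averaging them would raise r and change the figures, so the percentages are illustrative.
- **The carry-over figures are not a further harm.** They describe chance imbalance already contained in the raw test's SE. This is correct; they restate the same loss for a single trial.
- **Side-specific baseline scores are explicit only for the VAS.** For the dermatologist grade they are implied by the split-face design and grading at every visit, but not stated.
- **A linear model on a coarse ordinal grade is partly a preference.** The simulation on the actual grade steps kept the error rate near 5%, and the rank test can be kept alongside.
- **The text is in the past tense.** If results are known, the adjusted analysis is post hoc and must be labelled so.

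**Conclusion.** The concern holds. The plan specifies no baseline-adjusted active-versus-placebo comparison, and the tested variable, the index and the GEE are undefined. With randomised sides this is a loss of precision, not a source of systematic bias.

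The size cannot be derived from the documents. Under the assumed inputs, adjustment gains 27 points of power over raw scores at r = 0.73, 15 at 0.58 and 6 at 0.42, nothing at about 0.2, and loses about 1 point at zero. It beats change scores in every setting. The change should be made because it is cheap and the possible loss is small. Confidence is medium, since r is unknown and the raw-score reading is inferred.

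**What to change.** 1. State the variable used in each test, give the formula of the improvement index, and state the outcome, terms and use of baseline in the GEE.
2. For each post-baseline visit, regress the within-subject active-minus-placebo difference on the baseline active-minus-placebo difference. The intercept, at zero baseline difference, is the treatment effect.
3. If each subject receives one concentration, as the unpaired rank-sum test implies, add concentration as a centred between-subject term, so that high versus low is judged on the same placebo-controlled difference.
4. If the GEE is preferred, model this side difference, or enter the within-subject and between-subject parts of baseline separately. Do not enter own-side baseline alone.
5. Keep the signed-rank test as a sensitivity analysis.
6. If results are already known, label the adjusted analysis as added later.

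The cost is SAP wording and a few lines of R, with no new data provided the baseline grades were recorded for each side, as the design implies. The baseline term uses one degree of freedom; if r is near zero there is no gain and about 1 point of power is lost.

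### Does the SAP need to define what its bar plots and standard-error bars represent?

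*Combined protocol and SAP*

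**What the plan says.** Section 2 (Design) sets up a within-subject comparison: "A split-face design was employed to compare the effects of microneedle patches with and without anti-wrinkle ingredients". The same section has two blinded dermatologists grade the wrinkles at each visit, "calculating the wrinkle improvement index". Section 3.4 adds a 0 to 10 self-rated VAS and asks subjects "to record separate scores for the left and right sides".

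The Statistical Analysis Plan names one-tailed Wilcoxon signed rank tests at the 0.05 level, 95% confidence intervals, and GEE for change over the trial. For dose it says: "Wilcoxon rank sum tests compared different concentrations of active ingredients". On figures it says "Results were visualized with bar plots using the R-packages" it lists, "with standard errors presented as error bars". It does not state the endpoint, the summary statistic, the grouping of bars, the number of subjects or the quantity to which the standard error belongs. No other section supplies these.

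**The concern.** At least five quantities could sit behind a bar: the wrinkle grade or VAS on each side, a change from baseline, the improvement index, a GEE estimate, or the active-minus-placebo difference within a subject. The standard error means something different for each.

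In a parallel-group trial, a reader can combine two arm-level standard errors and get roughly the uncertainty of the comparison. In a split-face trial that fails, because the two sides belong to the same person and their correlation enters the calculation. The comparison of concentrations, in contrast, is tested as unpaired, and separate group standard errors would be the right ones for it. One undefined error bar cannot serve both comparisons.

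Bar plots are the only figures the plan names. If they show per-side means without saying so, a reader who judges the split-face result by how the bars overlap could get the wrong impression of its precision.

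**Working it through.** The plan states no sample size, SD, effect size or correlation, so it has no figure of its own to reproduce. The check has two parts.

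**1. How far per-side error bars could mislead.** Assumptions, none of them in the documents: both sides have the same SD *s*, there are *n* subjects, and the correlation between a subject's sides is ρ.

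- Per-side SE = *s*/√*n*.
- Variance of the within-subject difference = *s*² + *s*² − 2ρ*s*² = 2*s*²(1 − ρ), so its SE = *s*√(2(1 − ρ))/√*n*.
- SE inferred by treating the two bars as independent = *s*√2/√*n*.
- Ratio A, paired SE to per-side SE = √(2(1 − ρ)).
- Ratio B, independent-bars SE to paired SE = √2/√(2(1 − ρ)) = 1/√(1 − ρ).

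| ρ (assumed) | Ratio A | Ratio B |
|---|---|---|
| 0 | √2.0 = 1.41 | 1.00 |
| 0.3 | √1.4 = 1.18 | 1.20 |
| 0.5 | √1.0 = 1.00 | 1.41 |
| 0.7 | √0.6 = 0.77 | 1.83 |
| 0.9 | √0.2 = 0.45 | 3.16 |

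Ratio A shows that a single per-side bar can be too short or too long as a guide to the contrast. Ratio B shows that, over this range, a reader who combines the two bars as if independent never makes the contrast look more precise than it is. At positive correlations that reading understates its precision. If the bars show within-subject differences, both ratios are irrelevant.

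**2. What in the plan depends on the bars.**

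- *Signed rank test.* It ranks within-subject differences, so the pairing is built in. It uses no plotted standard error.
- *95% intervals.* They are calculated as a separate item and are not read from a figure.
- *Rank sum test for concentrations.* It uses ranks from separate groups and again takes nothing from the figure.
- *GEE.* It produces its own estimates and standard errors.

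None of the four takes the bar plot as an input. Redefining the bars would leave every p-value, interval and estimate as it is.

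**The case for a change.** The best case for acting is that this plan chose to specify the plot type, the software and the kind of error bar. Having said that standard errors are shown, it should say of what. The split-face design makes that more than pedantry, for the reason in the table above. The plan also does not say which quantity its 95% intervals are for, so a reader cannot assume that an interval for the paired contrast will accompany the bars. The remedy would be cheap: a sentence or two and one added plot from data already collected.

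Much of this stands as description. The sentence is incomplete, no other section completes it, and the arithmetic is right under its assumptions. Three things keep it from requiring a change.

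- Axis labels and captions exist to say what a bar is, and the analyst supplies them when drawing the figure. The documents contain no results figures, so nothing shows that labels would be absent or that per-side means would be plotted.
- The unstated target of the intervals is a question about endpoint and contrast. Defining the bars would not settle it.
- An added plot of within-subject differences is a reasonable preference in reporting, but it alters no result.

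One could go further and convert touching bars into p-values across the assumed correlations. Those would come from a normal test on means, whereas the plan uses a signed rank test on grades or VAS scores. They are not p-values this trial would produce, and they carry no weight here.

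**Conclusion.** The gap is real but confined to presentation, and no change to the plan follows. The figure sentence leaves the plotted quantity open, and analysts fill that in routinely through the figure's label and caption. The effect on tests, intervals, estimates and conclusions is nil.

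The possible effect on a reader's impression is the factor √(2(1 − ρ)), from 1.41 down to 0.45 for ρ from 0 to 0.9. It arises only if the bars are per-side means with equal standard errors and are left unlabelled. The correlation is assumed throughout. It remains true that a per-side standard error does not show the precision of the active-minus-placebo contrast, and whoever captions or reads the figures should keep that in mind.
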